[figure not shown]

Study title	REtinaL Imaging & Ambulatory BLOOD PrEssure: validating ultra-widefield retinal imaging derived biomarkers against ambulatory blood pressure (RELIABLE)
Co-sponsors	The University of Edinburgh and NHS Lothian
Study Protocol version Number and Date	Version 2.0 04th December 2018
Statistical analysis plan version Number and Date	Version 1.0. 14 th February 2020
ClinicalTrials.gov identifier	NCT04118205
Sponsor number	AC18080
IRAS project number	228069
Chief Investigators	Approved
[name] NHS Lothian [contact]	Signature and date
[name] NHS Lothian [contact]	Signature and date
Sponsor representative	
[name] Head of Research Governance, ACCORD NHS Lothian [contact]	Signature and date
Funder representative	
[name] [name] Optos plc [name]	Signature and date  Signed by: [name] Date: 14 Feb 2020 14:55:25 +00:00 Reason: Approved By DocuSign

Primary Objective

Arterial to venous ratio (AVR) measurements from the left eye (semi-automated and automated) will be investigated against clinic blood pressure (average of 4 measurements) for performance of classification of hypertensive status (based on gold standard; daytime mean ambulatory systolic blood pressure).

Dependent variable

Hypertensive status. Hypertension defined as daytime average ambulatory systolic and/or diastolic blood pressure (ABPM) measurement greater than or equal to 135/85 mmHg, respectively.

Independent variables

AVR; semi-automated and automated measurements in both right and left eyes. These measurements are obtained using computer code, please see appendix for details of the method. Also in the appendix are the secure hash algorithm (SHA) checksums of the code and results, which enables anyone to verify the code that is used is exactly the same as when the checksum was created.

Clinic blood pressure (CBP); average of four readings, two per arm.

Primary analysis

Demographics of the sample will be described. Descriptive statistics for quantitative parameters will be presented as mean, standard deviation (SD); or median and inter-quartile range (IQR) for skewed data.

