Simple comparison analyses will be performed between those with and without hypertension, and those who are under treatment for hypertension vs those who are not, for each of the included variables. Univariate analyses will be completed using either a Pearson chi-square (for categorical variables) or independent samples t-test (for continuous variables). A p value of < 0.05 will be used to demonstrate a statistically significant difference.

Receiver operating characteristic (ROC) curves and area under the curve (AUC) estimates will be estimated for the prediction of hypertensive status.

In the primary analysis AVR measurements from the left eye (semi-automated and automated) will be investigated against clinic BP (average of 4 measurements) for performance of classification of hypertensive status (based on gold standard; daytime mean ABPM) measured by AUC. We have pre-specified hierarchical primary endpoints in the table below;

Exclusion criteria

The following data will be excluded from the analysis:

- Insufficient ABPM measurements; less than 70% successful daytime readings.
- Retinal image of inadequate quality for determination of AVR as defined in the appendix.

Step 1	Non-inferiority of semi-automated AVR measurements from the left eye (where unavailable, measurements from the right eye will be used) against CBP for predicting hypertensive status in the full sample where semi-automated AVR measurement is defined. If significant at $p < 0.05$ move on to Step 2
Step 2	Non-inferiority of automated AVR measurements from the left eye (where unavailable, measurements from the right eye will be used) against CBP for predicting hypertensive status in the full sample where automated AVR measurement is defined. If significant at $p < 0.05$ move on to Step 3
Step 3	Non-inferiority of semi-automated AVR measurements from the left eye (where unavailable, measurements from the right eye will be used) against CBP for predicting

	hypertensive status in the untreated sample where semi-automated AVR measurement is defined. If significant at $p < 0.05$ move on to Step 4
Step 4	Non-inferiority of automated AVR measurements from the left eye (where unavailable, measurements from the right eye will be used) against CBP for predicting hypertensive status in the untreated sample where automated AVR measurement is defined.

Hierarchical primary objectives each tested only if the preceding tests were significant.

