Untreated patients are those who are not on any antihypertensive therapy at the time of ambulatory blood pressure monitoring.

The non-inferiority of retinal classification of hypertensive status compared with clinic blood pressure will be estimated using MedCalc and the R open source software based on one-sided Z-test. We will use a non-inferiority margin (Δ) on the AUC of 0.05. (This is the difference between the optimum method for combining multiple automated office blood pressure measurements, relative to ABPM, and a single blood pressure measurement [5].), P-values will be determined with a Wald-test.

The hierarchical analysis will negate the need to adjust p values.

Secondary analysis:

Right eye AVR for predicting hypertensive status.

Average of left and right eye AVR for predicting hypertensive status.

Regression analysis of AVR with ABPM as a continuous variable.

Using night-time mean ABPM as reference standard instead of daytime ABPM.

Using 24-hr mean ABPM as reference standard instead of daytime ABPM.

AVR and demographic info (age, sex, BMI, medication) for predicting hypertensive status.

Clinic BP and demographic info (age, sex, BMI, medication) for predicting hypertensive status.

Totally automated analysis (with automated instead of AB testing for image quality).

Tables

Table 1: Study sample and group comparison

Table 2: Logistic regression and ROC analysis results

Figures:

ROC curves for each of the models run

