- [5] Myles N Moore, Martin G Schultz, Mark R Nelson, J Andrew Black, Nathan B Dwyer, Ella Hoban, Matthew D Jose, Wojciech Kosmala, Monika Przewlocka-Kosmala, Jowita Zachwyc, Petr Otahal, Dean S Picone, Philip Roberts-Thomson, Panagiota Veloudi, James E Sharman, Identification of the Optimal Protocol for Automated Office Blood Pressure Measurement Among Patients With Treated Hypertension, *American Journal of Hypertension*, Volume 31, Issue 3, March 2018, Pages 299–304, <https://doi.org/10.1093/ajh/hpx180>

Checksums

Repository	Git commit checksum
Auto a (data files for outer measurement area)	7a0569f7d0866a6a7f0ff8d796e8292029609e68
Auto b (data files for inner measurement area)	875cda3a0c47207d11dcde93e8703911604a5f76
Semi a (data files for outer measurement area)	e8c08162c23d051e74b7c2c1193cb1d4c4432a06
Semi b (data files for inner measurement area)	c7628d80bc852c349d7e35b4f8c79eabd81da477
Ab testing: code for performing AB testing	458c9881691b76502e3e0ccddd90bb19986da765
Annotation (GUI for manual correction)	9b33115fad2c3b4ecc2342620ce4ec6607ca2d29
Auto (Auto analysis code)	2f291c84fc61aff7babe90ae1dbff27938d08f49
Avr (Semi automated analysis code)	37d281df2c925a75b545aab35ce79db5cbc2179b
Odfovea (manual OD and fovea annotation)	8134f48ada6d3bead4faf23846375eb753691117
Projection (Stereographic projection code)	983415ece2b38f1559817a35f4825d0774e46211
Scripts (code)	c8ac3f9a12ddd80e32f989eb6e5e53c58aff15d9
Sort (code)	868fd71cb355e4a480a172f360485f2629f32bdd
Results for stats (excel sheets with results for [name])	c3cf652e960f4dba5210c2f81bd892fd09dd9ccd
Odfovea auto (Automated OD and fovea detection)	2fec5fb0c2962695f5c8df11e1e9e9f89ab3e9da
Filename	SHA-256 Checksum
reliable_git_repo.zip (a zip folder containing the above git repos minus data files)	bb0c6f519e8a315039576a2fdc61525c3c94951f2628ec0a5d0d8e08c89f65fd
reliable_results_a.zip (a zip folder containing the outer area data files)	eaf7fca57db2e04a53b2d5e84d499a584ea57937ed293ab53a10cf04b2064f0e
reliable_results_b.zip (a zip folder containing the inner area data files)	ca4a4a3b4533a33cf01368b64dd7b4790cec505253aba5da394eede50d1f8eae

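### Does a margin of 0.05 taken from a treated-hypertension source need a further check before it is used in the untreated sample of Steps 3 and 4?

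*SAP*

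**What the plan says.** Under "Primary analysis" the SAP states "We will use a non-inferiority margin (Δ) on the AUC of 0.05". The reason follows in brackets: the figure is "the difference between the optimum method for combining multiple automated office blood pressure measurements, relative to ABPM, and a single blood pressure measurement", with reference [5] as its source. The reference list in the Appendix gives that paper's title as "Identification of the Optimal Protocol for Automated Office Blood Pressure Measurement Among Patients With Treated Hypertension".

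The same margin serves every row of the hierarchical table. Steps 1 and 2 use the full sample. Step 3 concerns "hypertensive status in the untreated sample where semi-automated AVR measurement is defined", and Step 4 tests automated AVR "against CBP for predicting hypertensive status in the untreated sample where automated AVR measurement is defined". The definition below the table reads "Untreated patients are those who are not on any antihypertensive therapy at the time of ambulatory blood pressure monitoring".

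The comparator is defined under "Independent variables": "Clinic blood pressure (CBP); average of four readings, two per arm". Of the eight items under "Secondary analysis", one pairs clinic BP with demographic information. None sets a single reading against the average, and none looks at the margin by treatment status.

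**The concern.** The margin's meaning comes from its benchmark: AVR may lose no more AUC than is lost by taking one office reading instead of the best combination of several. Going by the title, that benchmark was measured in treated patients, who are by definition absent from Steps 3 and 4. The SAP gives no reason for carrying the figure across, although it treats therapy as important enough to define two separate steps.

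The gain from averaging depends on the spread of blood pressure and on how far office and ambulatory values disagree, and both could differ with treatment. If the gain in untreated people were below 0.05, a pass at Step 3 or 4 would tolerate a larger loss than the benchmark implies; if above, the test would be stricter than it. The trial takes four readings per participant, so it seems natural to ask for an internal check.

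**Working it through.** **Can the 0.05 be reproduced?** No. The SAP gives neither of the two AUCs whose difference it is said to be, and it states no sample size, expected AUC or power. The figure can be neither confirmed nor refuted. What can be examined is how far such a benchmark might move between populations.

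**Model (every input assumed).** Daytime systolic ABPM is T ~ N(μ, sT), with hypertension when T ≥ 135. Clinic reading j is T + B + e_j, where B ~ N(0, sB) is the person's office–ambulatory discrepancy and e_j ~ N(0, se) is reading error. For the mean of k readings,

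AUC(k) = E[Φ((T₁ − T₀) / √(2(sB² + se²/k)))],

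where T₁ is drawn from the hypertensive and T₀ from the normotensive. The benchmark is gain = AUC(4) − AUC(1).

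**Calibration to a gain of 0.05** at μ = 135, sT = 10 mmHg:

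| sB | se | AUC, 1 reading | AUC, 4 readings | Gain |
|---|---|---|---|---|
| 6 | 7.38 | 0.842 | 0.892 | 0.050 |
| 8 | 8.93 | 0.799 | 0.849 | 0.050 |
| 10 | 10.93 | 0.759 | 0.809 | 0.050 |

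**Moving the population, reading error held fixed:**

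| What changes | Range of gain over the three calibrations |
|---|---|
| μ 125–140, sT 8–12 | 0.040–0.055 |
| μ 125–140, sT 6–16 | 0.030–0.058 |
| sB shifted by 2 mmHg either way | 0.038–0.063 |
| sB anywhere in 4–14 | 0.017–0.093 |

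The widest range joins extremes of different calibrations: 0.017 needs sB to go from 6 to 14, and 0.093 needs it to go from 10 to 4. A separate uncalibrated run (prevalence 0.3 or 0.5, ABPM SD 8–16, person-level SD 8 or 12, reading-error SD 5–10) gave 0.009–0.059. The benchmark therefore depends on the population, but nothing in the SAP says which way, or how far, untreated people differ from treated ones. The model is also systolic only, whereas the SAP defines status by systolic and/or diastolic pressure.

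**What would an internal check show?** The natural one is the four-reading AUC minus the mean of the four single-reading AUCs, paired, reading a 95% CI that excludes 0.05 as failure of the margin's basis. Its simulated SE is 0.0091–0.0094 at N = 100, 0.0059–0.0063 at 200 and 0.0042–0.0045 at 400 (N assumed). For a true gain of 0.040, the chance that the CI excludes 0.05 is approximately Φ(0.010/SE − 1.96):

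| N | SE | 0.010/SE | Chance of flagging |
|---|---|---|---|
| 100 | 0.0092 | 1.09 | 19% |
| 200 | 0.0061 | 1.64 | 37% |
| 400 | 0.0043 | 2.33 | 64% |

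A departure of 0.01 would thus be called a failure or not largely according to N.

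**Would a flag mean what it says?** The source's contrast is between an optimum combination of automated office readings and one reading. The trial's comparator averages two readings from each arm and is not described as automated or as that optimum. A gain other than 0.05 could come from the device, the arms or the measurement routine while the cited basis stood intact.

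**The case for a change.** The strongest case for acting is that the SAP itself chose to state the margin's basis, so a mismatch with two of its four primary steps is a weakness in what it fixes and is not something left to the protocol. A check would also be cheap: one secondary analysis outside the hierarchy, with the margin, alpha, order of steps and power untouched. Its blood-pressure part could be computed without AVR data, and it would be fairly precise: even at N = 100 the 95% half-width is about 1.96 × 0.0092 = 0.018.

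The textual facts stand, and so does the point that the SAP gives no reason for the transfer. The consequence does not. Steps 3 and 4 claim only that the AUC loss against the four-reading average is under 0.05; the SAP promises no comparison with a single reading. Since the check would alter no test, its only product is commentary on the margin, and a rule declaring the basis failed could put an unsupported sentence in the report. The source's population is known here only from a title, and the check also assumes that the four readings were stored individually, which the SAP does not state.

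**Conclusion.** No change to the plan is needed. One margin is fixed numerically in advance, with a stated basis and a citation, and an analyst following the SAP reaches a well-defined conclusion at each step. That the source studied treated patients leaves the justification thin for Steps 3 and 4, and only in part for Steps 1 and 2, which pool treated and untreated people. It does not show 0.05 to be wrong there, and the direction of any mismatch is unknown.

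Under the assumed model, moderate population differences move a 0.05 benchmark to roughly 0.04–0.06; only large shifts in the office–ambulatory discrepancy reach 0.017 or 0.093. Steps 3 and 4 are in any case tested only if Steps 1 and 2 succeed. Resetting the margin from the trial's own data would undermine the test, and a descriptive comparison would approximate the source's contrast without settling whether it applies. Naming the optimum method and acknowledging the treated source would help readers of the report, but that is an editorial courtesy. The conclusion rests on the SAP alone, with every blood-pressure input and every N above assumed.

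### The two covariate-adjusted secondary models would report AUCs scored on the same participants that fitted them, with no correction for optimism

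*SAP*

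**What the plan says.** The SAP's Secondary analysis section lists two multi-predictor analyses: "AVR and demographic info (age, sex, BMI, medication) for predicting hypertensive status" and "Clinic BP and demographic info (age, sex, BMI, medication) for predicting hypertensive status". The outputs are "Table 2: Logistic regression and ROC analysis results" (Tables) and "ROC curves for each of the models run" (Figures). The Primary analysis section sets the measure of performance: "Receiver operating characteristic (ROC) curves and area under the curve (AUC) estimates will be estimated for the prediction of hypertensive status".

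The primary comparison uses AVR and clinic BP each on its own, "for performance of classification of hypertensive status (based on gold standard; daytime mean ABPM) measured by AUC".

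For the two adjusted models the SAP names no bootstrap, cross-validation, split sample, shrinkage or externally fixed coefficients. The Appendix does mention a validated algorithm and a separate training set, but both concern vessel segmentation, not the prediction of hypertension. The protocol is not at hand.

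**The concern.** Each adjusted model has at least five fitted slopes: the marker and four covariates, more if medication has more than two levels. Maximum likelihood tunes these slopes to the sample. Scoring the AUC in that same sample rewards the tuning, so the apparent AUC exceeds, on average, what the same coefficients achieve in new participants. This happens without any variable selection.

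A single-marker AUC depends only on ranks and has no fitted weights. It is free of this bias if the direction of AVR is fixed in advance and clinic BP enters as one variable. The SAP states neither; it describes clinic BP only as "Clinic blood pressure (CBP); average of four readings, two per arm".

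Both kinds of AUC would appear in the same planned outputs. A reader will naturally set AVR alone beside AVR plus demographics and read the difference as the value of the demographics. That difference is overstated and can have the wrong sign.

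**Working it through.** **Inputs.** From the SAP: two models, the four covariates, AUC as the measure, and the primary margin ("We will use a non-inferiority margin (Δ) on the AUC of 0.05"), used here only as a yardstick because it does not apply to these models. The SAP states no sample size, number of hypertensives, prevalence or expected AUC, so there is no figure of its own to reproduce. Everything below is assumed.

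**Definitions.**
- Optimism = mean apparent AUC − mean AUC of the same coefficients in new participants.
- Gain = AUC of the adjusted model − AUC of the marker alone.

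**Main simulation.** 1,000 data sets per setting, each scored on 5,000 new participants, with five slopes per model and prevalence about 50% and 30%. Markers are independent of demographics given status. Log-odds for age/sex/BMI/medication are 0.1 each (weak), 0.3/0.4/0.3/0.4 (modest) or 0.6/0.6/0.5/0.6 (strong). AVR/clinic BP AUCs are 0.70/0.75, 0.72/0.75, 0.75/0.75 and 0.75/0.80 (inside the margin), and 0.60/0.75 and 0.56/0.75 (far outside). Monte Carlo standard error is at most 0.002.

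| | n = 100 | n = 200 | n = 300 | n = 500 |
|---|---|---|---|---|
| **AVR within 0.05 of clinic BP** | | | | |
| Optimism, AVR model | 0.032–0.065 | 0.018–0.034 | 0.011–0.023 | 0.007–0.014 |
| Optimism, clinic BP model | 0.029–0.054 | 0.014–0.028 | 0.010–0.019 | 0.006–0.011 |
| Bias in AVR-minus-clinic-BP difference | −0.003 to +0.013 | −0.002 to +0.008 | −0.001 to +0.006 | −0.001 to +0.003 |
| **AVR far outside** | | | | |
| Optimism, AVR model | 0.048–0.116 | 0.026–0.075 | 0.017–0.055 | 0.011–0.036 |
| Bias in difference | +0.013 to +0.062 | +0.008 to +0.047 | +0.005 to +0.037 | +0.003 to +0.026 |

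With AVR's direction fixed, optimism for AVR alone or clinic BP alone was at most 0.004, within simulation error.

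**Gain from adding demographics to AVR** (AVR AUC 0.70, prevalence 50%):

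| | n = 100 | n = 200 | n = 300 | n = 500 |
|---|---|---|---|---|
| Weak: apparent | +0.034 | +0.019 | +0.014 | +0.010 |
| Weak: new data | −0.024 | −0.010 | −0.006 | −0.002 |
| Weak: overstatement | 0.058 | 0.029 | 0.020 | 0.012 |
| Modest: apparent | +0.063 | +0.049 | +0.045 | +0.040 |
| Modest: new data | +0.012 | +0.024 | +0.027 | +0.031 |
| Modest: overstatement | 0.051 | 0.025 | 0.018 | 0.009 |

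Overstatement is apparent minus new-data gain, for example 0.034 − (−0.024) = 0.058.

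**Sensitivity.** With markers correlated 0.3 with age and BMI (0.70/0.75, modest effects), the apparent gain is +0.034 / +0.021 / +0.018 / +0.014 and the new-data gain −0.014 / −0.002 / +0.002 / +0.005.

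**A separate simulation** (400 data sets, 20,000 new participants, 50% prevalence) with a marker of AUC 0.609 and null covariates gave, at n = 100, apparent 0.659 and new-data 0.569, so optimism 0.659 − 0.569 = 0.090. The apparent gain was 0.053 and the true gain 0.569 − 0.609 = −0.040. With a marker of AUC 0.815 and null covariates, optimism was 0.831 − 0.802 = 0.029 at n = 100 and 0.821 − 0.807 = 0.014 at n = 200. Across all its multi-predictor settings the apparent AUC exceeded the new-data AUC in 65% to 99% of data sets.

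**Check of the remedy** (bootstrap correction, 400 data sets, 100 refits each, n = 100, 200, 500). At 0.70/0.75 the corrected AUC was within −0.001 to +0.006 of the new-data AUC for both models. In the weakest case (0.56/0.75, weak demographics) the AVR model's apparent/new/corrected AUCs were 0.644/0.539/0.566, 0.615/0.549/0.564 and 0.591/0.560/0.564. The corresponding between-model differences were −0.126/−0.189/−0.160, −0.150/−0.193/−0.179 and −0.167/−0.188/−0.184. The share of bias in the difference that is removed is 0.034/0.063 = 54%, 0.029/0.043 = 67% and 0.017/0.021 = 81%.

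**The case against.** The strongest reply is that this is silence rather than error. The SAP gives each adjusted model one line, does not say the AUC will be uncorrected, and plans no test of the gain from demographics. The contrast a reader might most reasonably draw, between the two adjusted models, has the same covariates on both sides and is nearly unbiased when AVR is close to clinic BP. Where the bias in that contrast is large, AVR is so much weaker that it would still look clearly inferior (apparent difference −0.126 at n = 100 in the weakest case). Sampling error also matters: by Hanley–McNeil at AUC 0.75 and 50% prevalence, one AUC has a standard error of about 0.049 / 0.034 / 0.028 / 0.022 at n = 100 / 200 / 300 / 500. From n = 200 upward the inside-margin optimism does not exceed one standard error.

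Much of this stands as a limit on importance. The size cannot be fixed from the SAP, and a reversal of sign needs weak covariates, or correlated ones at n of 200 or less. It does not remove the point. The SAP does fix the models, the table and the figures. Without a named correction, the default reading is the apparent AUC. A systematic upward bias is not excused by being smaller than random error, since the confidence interval does not allow for it.

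**Conclusion.** The concern holds, as a minor point. As written, the two adjusted AUCs are apparent values, biased upward on average and not like for like with the single-marker AUCs. For AVR within 0.05 of clinic BP, the AVR model's mean optimism ranges from 0.032–0.065 at n = 100 down to 0.007–0.014 at n = 500. At n = 100 it can exceed the 0.05 that the SAP uses as its primary margin. It is larger if AVR is a weak marker.

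These sizes depend on the assumed sample size, prevalence, marker AUCs and covariate effects. The direction of the bias does not: it was upward on average in every setting. The comparison between the two adjusted models, which the SAP does not formally make, is materially distorted in favour of AVR only if AVR is much the weaker marker. Steps 1 to 4 of the primary hierarchy use single markers and are unaffected by this point.

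**What to change.** For these two models only:

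- Report a bootstrap optimism-corrected AUC in Table 2 beside the apparent AUC. Refit the whole model in each of at least 500 resamples. Take each refit's AUC in its own resample minus its AUC in the original data, average these, and subtract the average from the apparent AUC.
- Label the two ROC curves as apparent.
- If the two models are compared, correct the AUC difference using the same resamples.
- Do not set an uncorrected adjusted AUC against a single-marker AUC.

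The cost is a few lines of R, which the SAP already names, and one extra column in Table 2. No new data are needed and the primary analysis does not change. The reported AUCs of the two models will fall by roughly the optimism shown above: little at n = 500, more in a small sample or with a weak marker. The correction is incomplete for a very weak model in a small sample (0.566 corrected against 0.539 in new participants at n = 100 in the weakest case), and the report should say so if that situation arises.
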